Blood Volume Analysis - Guided Heart Failure Management

NCT04111185

Document Date: February 24, 2020

1. Protocol Title

Blood Volume Analysis- Guided Heart Failure Management

2. Background

Heart failure (HF) is a leading cause of morbidity and mortality in the US. Simply put, the numbers are alarming. HF affects more than 6 million adults in the United States (US) alone.¹ It is the most common cause of hospitalization among Medicare beneficiaries and outcomes remain unacceptably poor. The key hallmark of acute heart failure (HF) is vascular congestion. Despite its central role in the pathophysiology of HF, our understanding of congestion remains limited. The current HF pathophysiologic model suggests that congestion is the result of volume retention, and therefore therapies (such as diuretics and ultrafiltration) have generally targeted a suspected volume overload. Despite this, the therapeutic benefits of fluid removal strategies on short and long term outcomes have been modest or absent. More recently the concept of fluid gain as cause of cardiac decompensation has been challenged. Our recent work proposed a new concept of cardiac congestion and decompensation, which may play a critical role in the pathophysiology of congestion in a significant portion of patients. This disruptive concept suggests that cardiovascular congestion is the result of blood redistribution from the abdominal (splanchnic) compartment to the heart and lungs. To allow a personalized treatment of patients with HF it is imperative to understand whether a patient has fluid overload and if so to what extent. To date the assessments of congestion is often limited to surrogates of intravascular pressure and volume, which often provide an incomplete and, in some instances, a false impression of a patient's congestion status. Volume overload, based on clinical examination parameters (presence of jugular venous distension, peripheral edema and orthopnea, an S3 and positive hepato-jugular reflex)^{1, 2} increases in body weight,^{3, 4} natriuretic peptides⁵, estimates of plasma volume⁶ and even invasive hemodynamic measurements^{7, 8} lack sufficient sensitivity and specificity to accurately assess a patient's intravascular volume status. Yet, the use of blood volume analysis (BVA) via I131-labeled human serum albumin indicator-dilution technique, the gold-standard test to determine the intra-vascular volume, could overcome many of the limitations of conventionally used surrogate markers.

While it is well recognized that the extent of fluid volume congestion is closely associated with clinical outcomes,⁹⁻¹² the extent to which decongestion is achieved with diuretic therapy is highly variable and often less than clinically suspected.^{11, 13, 14} Our preliminary data supports that current surrogate markers of condestion lack accuracy to estimate the true blood volume.⁶ Given the limitations in clinical assessment of congestion and volume overload, an accurate assessment of blood volume using a standardized indicator-dilution technique with I-131-labeled albumin could provide distinct clinical benefit. This technique is considered to be the gold-standard for the guantitative assessment of plasma and total blood volume analysis given its precision, reproducibility, and clinical validity.¹⁷ Retrospective studies using this technique have

Figure 1: Heterogeneity in blood volume parameters. From Miller W, et al. *JACC HF* 2014

demonstrated marked heterogeneity in volume status in patients with acute and chronic HF^{11, 13, 15} and uncovered unrecognized subclinical hypervolemia in asymptomatic and symptomatic HF patients (**Figure 1**).^{15, 16} Most recent retrospective evidence now suggests that BVA- guided HF management could improve clinical outcomes such as HF rehospitalization and mortality in patients admitted with acute HF.¹⁶ Consistent with our paradigm shifting hypothesis and **preliminary data**, inappropriate redistribution of intra-vascular volume might be an additional important driver of cardiac decompensation and can explain an increase in central filling pressures in the absence of weight gain or total body volume increase ^{11, 17, 18}. Supportive evidence is provided by body volume analysis using the I131-labeled human serum albumin indicator-dilution technique. Using this technology studies found that chronic HF patients with persistent symptoms are in 35% of cases hypovolemic or euvolemic¹¹ and the same was even true for patients admitted for decompensated HF (34%).^{19, 20}

In an attempt to gather **preliminary experience** with the Daxor BVA technology, we enrolled and performed BVA measurements in 14 patients with acute and chronic HF within a 3 months window as part of a Duke approved IRB protocol (Pro00100536, [name]).

3. Purpose of the Study

Our objective is to develop personalized treatment approaches to the treatment of acute HF. The central hypothesis is that BVA will allow improved congestion phenotyping of acute HF patients given the ability to directly and accurately measure blood volume. Knowledge of specific congestion phenotypes will be the basis for targeted treatment algorithms. **The specific objectives are:**

Perform a pragmatic randomized pilot study (N=50) with blood volume analysis (BVA) – guided treatment strategy vs standard of care in patients admitted for acute decompensated HF *A*: Study effects of unblinded BVA results on provider treatment choices and clinical endpoints *B*: Develop a new BVA-guided treatment algorithm based on the observed experience with BVA at Duke

4. Design & Procedures

Perform a pragmatic randomized pilot study (N=50) with BVA- guided treatment strategy vs standard of care in patients admitted for acute decompensated HF.

The main intent for this pilot study is to gather information on optimal study design, treatment recommendations and sample size for a future planned pivotal trial.

Design: Pragmatic pilot study of patients admitted with acute HF. Upon enrollment patients will be randomized to either the unblinded arm (BVA- guided treatment), or blinded arm (Standard of care treatment), where BVA results will not be provided to patients or provider team. The study is planned to start in the Spring, 2020 and be open for enrollment for 1 year. (**Figure 2**)

Population: Patients presenting to Duke Hospital with a history of HF and worsening symptoms of HF will be enrolled in the study. Exclusion criteria are: Ongoing pregnancy, age <18 years, post heart transplantation or ongoing mechanical circulatory support, and end stage renal disease.

Treatment protocol: A pre-determined assortment of demographic and medical information will be gathered for all patients upon admission, 24h, 48h, 72h and upon completion of repeat BVA and upon discharge. See flow chart below (**Table 1**).

Table 1: Patient assessments during the study. SOC indicates standard of care and CS indicates clinical study related procedures.

Required Assessment	Baseline	Day 1	Day 2	Day 3	Day before discharge	Discharge	30 days post discharge
Consent/Randomization	X (CS)						
Medications	X (SOC)	X (SOC)	X (SOC)	X (SOC)	X (SOC)	X (SOC)	X (CS)
Vitals (BP, HR, RR, SpO2, weight)	X (SOC)	X (SOC)	X (SOC)	X (SOC)	X (SOC)	X (SOC)	
Orthostatic vitals	X (CS)				X (CS)	X (CS)	
Urine output	X (SOC)	X (SOC)	X (SOC)	X (SOC)	X (SOC)	X (SOC)	
Labs: BMP, NT- proBNP, urine sodium, CA-125	X (SOC/CS)	X (SOC/C S)		X (SOC/CS)	X (CS)		
BVA	X (CS)				X (CS)		
Dyspnea Questionnaire	X (CS)	X (CS)	X (CS)	X (CS)	X (CS)	X (CS)	X (CS)
Impedance and lung fluid content measurement	X (CS)				X (CS)	X (CS)	
Echocardiogram	X (SOC/CS)				X (SOC/CS)		
Pulse Wave Analysis	X (CS)				X (CS)		
Physician questionnaire	X (CS)				X (CS)		

Phone Call				Х
				(CS)

Following enrollment, subjects will undergo the following tests/measurements. Some procedures occur as part of standard of care testing (SOC) while some testing will be performed as part of the clinical study (CS). All of the following tests have been approved in the present combination in Pro00100536, PI: [name].

- **IV line** will be placed (SOC)
- If the subject is female and childbearing potential and has not had a **pregnancy test** since the arrival to the hospital, a blood pregnancy test will be done (SOC). If positive the subject will be excluded from the study.
- **Blood work:** Basic metabolic panel (BMP) (SOC), N-terminal pro-brain natriuretic peptide (NT-proBNP) (CS), urine sodium (CS), CA-125 (CS). This will require an extra lab draw. Expected blood loss is <20ml.
- **Blood volume analysis** The described BVA technique is an FDA approved technology for the purpose of volume measurement. It is currently used in clinical practice on patients with syncope, heart failure and sepsis to determine the exact intravascular volume and their components such as plasma volume and red blood cell volume.

BVA will be completed within 24h of admission and again within 24h before anticipated discharge. Each blood volume analysis will take about 60 minutes to complete. The agent will be delivered to the radiopharmacy and prepared by the radiopharmacy. The agent will be then transported and stored at the DMP/ Radiology. On the study day the agent will be taken from the DMP to the patient's room for the injection. An intravenous line connected to a 50 ml saline solution will be inserted in an arm. This line will be used to inject a small amount of diagnostic radioactive material into the patient's circulatory system. A second IV line will be placed to collect small samples of blood at timed intervals 15 min after injection of drug, then every 6 minutes for an additional 3 samples (18, 24, and 30 minutes). Blood collection timeframes do not have to be exact but time of blood draw will be documented. Approximately 15 ml of blood will be drawn total. The collected blood samples will be processed in the DMP in the device provided by the company.

On the report, values will be expressed as percentage (%) deviation from ideal volumes and the predicted normal BV was determined from patient's height, weight and deviation from ideal body weight. The output on the BVA results will be shared with the clinical teams within an hour of processing as outlined in **Figure 2.** BVA results will be provided only to patients and providers in the unblinded/BVA- guided arm. In the BVA- guided arm the medical team will also be provided with data to inform the medical management of their patients based on observed BVA results (admission and prior to discharge).

The current data supports that ideal patient-specific euvolemic target should be 8-10% above euvolemia. All recommendations will not be binding.

Further, if there is a red-cell deficit of >20% the team in encouraged to consider therapies to augment the red blood cell pool. Treatment is up to the physician discretion.

Similarly, the test might reveal red blood cell overload (polycythemia) which ideally is addressed by the medical team using whatever options are clinically available.

- **Vital Signs:** Recorded vital signs including weight, blood pressure, heart rate, respiratory rate, SpO2
- **Dyspnea questionnaire** using a 7-point Likert scale and Visual Analog Scale (CS)
- Orthostatic heart rate and blood pressure (5 minutes supine, 1+5 minutes sitting and 1+5 minutes standing) on the day before procedure if the subject is an inpatient and again within 1 hour before procedure (CS). Also we will document whether subjects have symptoms bending over for 10 seconds (bendopnea).
- Non-invasive Testing
 - Fluid Lung Content measurement of chest fluid content using the ReDS[™] unit (Sensible Medical, Tenafly, NJ). The ReDS unit is a vest that emits radiofrequency waves to measures fluid content. The device is FDA approved. The measurement requires 10 minutes.
 - **Impedance** for lung water volume measure using the Cardioset which uses electrical impedance technique to determine intra-thoracic blood volume.
 - Arterial stiffness assessment (Pulse Wave Analysis): We will use the Sphygmocor[™] (AtCor Medical, Itasca, IL) to measure arterial stiffness. It is measured through a brachial cuff. This measurement requires 5 minutes.
- **Bedside ultrasound** will be performed of the heart and abdomen. We will assess: left ventricular function, inferior vena cava dimensions and collapsibility.

A phone call at 30 days will evaluate the vital status of the patient, potential changes in medications after discharge, and assess the patient's symptoms via the standardized questionnaires.

Physicians will be interviewed with a questionnaire at the time point of the BVA testing. The questionnaire will explore whether the unblinded BVA results changed the perception of the patients' congestion status and if they will result in a change in management.

Randomization process: Randomization will be performed by the study coordinator using computer software.

Potential complications:

 The radiation effective dose from a single administration of I-131 albumin for blood volume measurement is 0.60 mSv which is equal to three chest x-ray exams. It is equivalent to about 2 months of natural background exposure.

5. Selection of Subjects

For this study we seek to enroll heart failure patients admitted for acute decompensated heart failure to the cardiology service at the Duke Hospital. All patients irrespective of gender, race, and ethnicity will be considered for the study.

Exclusion criteria are:

- Ongoing pregnancy
- age <18 years
- Recent acute MI or hemodynamic instability: Acute MI (STEMI or Type I NSTEMI) within 7 days
- post heart transplantation or ongoing mechanical circulatory support
- Progressive cardiogenic shock

- Patients with Ventricular Assist Devices
- End stage renal disease

6. Subject Recruitment & Compensation

Potential subjects will be identified via two potential pathways.

Inpatients will be identified within 24 h of the admission via screening of the admission logs and inpatient census. Consent process will occur in the subjects' hospital rooms on Duke Hospital Divisions 7700/7100/7300/7200/3100/3300/7 East.

Patients considered for this study will be identified within 24 h of admission. Prior to approaching the patient we will discuss the patient and his/her eligibility with the primary cardiology team. Study team will be introduced by the primary team. Ample time will be given to the patient to review the consent and have all questions answered. After the patient has consented to the study we will begin study related activities. The primary enrollment target is up to =50.

Subjects will be informed that their participation is strictly voluntary. They will be assured that the decision to decline participation will have no impact on their care or the perceptions of their providers.

The subject will be compensated \$100 for participation in this clinical study.

7. Consent Process

Candidate subjects will be informed of the risks and benefits of participation in the study. They will be informed of the study process and demands. They will be given a copy of the informed consent document to review and afforded adequate time to do so.

Informed consent will be obtained prior to the study. Consent will be obtained by the study Principal Investigator (PI), Duke Heart Center study coordinators who are trained on the study and who have been trained on the informed consent process, and other key personnel as designated by the PI. Consent will be obtained in the subjects' rooms. A subject is considered enrolled in this clinical study at the time at which the subject and investigator or authorized designee have personally signed and dated the Informed Consent Form.

8. Subject's Capacity to Give Legally Effective Consent

Subjects must to be able to understand the English language and understand the study process, including all potential risk and benefits. Any subject for whom the study personnel or treatment team has cause for concern regarding the subject's ability to understand the study process or follow the consent process, will be excluded from the study.

9. Study Interventions

- Lab draws
- Vital signs
- Orthostatic vital signs
- Non-invasive imaging with ultrasound
- Non-invasive hemodynamic monitoring (heart rate variability, Sphygmocor ReDS,

Cardioset)

- Blood volume analysis

10. Risk/Benefit Assessment

This study is associated with only small risks and has the potential to provide significant insight into the physiology of the patient's congestion. Risks are limited to the intravenous line placement, and radiation exposure.

Anticipated benefits to the subject include detailed information on congestion status and extent of fluid overload, otherwise not captured with standard clinical care diagnostic methods. This newly obtained data will be provided back to the patient and provider which then can result in a change in clinical care. However the study or protocol does not have an influence on the clinical care the patient will receive as a result of the newly obtained information.

11. Costs to the Subject

Study-specific activities and assessments will be conducted at no additional cost to the subject. Subjects will still be responsible for standard of care procedures related to hospitalization for heart failure.

12. Data Analysis & Statistical Considerations

Descriptive statistics of continuous outcomes will include sample size, mean, median, standard deviation, minimum and maximum. For categorical outcomes, the number and percentage of subjects in each category will be presented. Statistical comparisons will be made using t-tests for continuous outcomes and chi square or Fisher's exact test (depending on overall event rates) for categorical outcomes.

13. Data & Safety Monitoring

Significant adverse events associated with the study procedures are not expected. 30 day follow-up is planned. Should complications be encountered, they will be reported to the IRB within 10 working days or per IRB policy. The Principal Investigator will also provide an annual report of any side effects or problems to the IRB during the study renewal process.

No protected health information associated with the study procedures will be sent outside of Duke. PHI (subject ID, height, weight, and gender) will be used internally for measuring the blood volume. Additionally, we will capture the birth year of the patient to perform the pulse wave analysis.

14. Privacy, Data Storage & Confidentiality -

Data will be obtained by approved study personnel. An enrollment log will also be maintained in an Excel Spreadsheet on the Heart Center's secured S:drive. The subject ID will also be stored on the folder to track subject enrollment and collection of data. Data will be recorded in Excel. Only deidentified data will be available for statistical analysis. All subject identifiers will be removed for database storage, statistical analysis and data reporting. This data will be stored on a study specific folder on the Duke server behind the Duke firewall. The subject ID code will be destroyed after data analysis is completed. Protected health information will not be used for any other purposes than those described in this protocol without obtaining further IRB approval. This information will be used for research purposes only and subjects will never be contacted regarding information obtained through chart review. A designated statistician from the DCRI will provide support with statistical analysis.

The adequacy of the Research Data Security Plan (RDSP) will be evaluated and approved by the Cardiology CRU prior to study conduct.

Any publications or presentations that result from this research will not identify any subjects individually, and will present data in aggregate form only.

Gathered data will be stored for at least 6 years.

References

1. Stevenson LW and Perloff JK. The limited reliability of physical signs for estimating hemodynamics in chronic heart failure. *JAMA : the journal of the American Medical Association*. 1989;261:884-8.

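### Section 12 does not say how the 7-point Likert dyspnea score is tested; the categorical route would cost about half the power of an ordinal test, and neither stated test uses the baseline score

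*Combined protocol and SAP*

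**What the plan says.** Section 4 collects dyspnea "using a 7-point Likert scale and Visual Analog Scale (CS"). Table 1 schedules the "Dyspnea Questionnaire" at baseline, days 1, 2 and 3, the day before discharge, discharge, and 30 days after discharge: seven occasions, the first of them before any guided treatment.

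Section 12 is the whole statistical plan. On description it says "For categorical outcomes, the number and percentage of subjects in each category will be presented". On inference it says "Statistical comparisons will be made using t-tests for continuous outcomes" and "chi square or Fisher's exact test (depending on overall event rates) for categorical outcomes". It names no ordinal or rank method and no covariate. For dyspnea it gives no time point for the comparison and does not say whether a change score is meant.

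On size, Section 4 describes the work as: "Perform a pragmatic randomized pilot study (N=50) with BVA- guided treatment strategy vs standard of care in patients admitted for acute decompensated HF". Section 6 adds: "The primary enrollment target is up to =50". On allocation, Section 4 says only: "Randomization will be performed by the study coordinator using computer software". The documents state no allocation ratio, significance level, power or effect size, and they give no anchors or direction for the Likert item.

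**The concern.** A 7-point Likert response consists of ordered categories. Section 12 sorts outcomes into continuous and categorical and has no place for ordered ones, so an analyst could defend either route.

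On the categorical route the analysis is a 2×7 table with about 25 patients per arm. Pearson's chi-square, or Fisher's exact test extended to seven columns, then looks for any difference in pattern over up to 6 degrees of freedom and ignores the order of the categories. A treatment that moves patients consistently towards less dyspnea is the kind of effect such a test detects poorly. Its p-value also comes with no single measure of effect. Section 4 says that the pilot is meant to inform the sample size of a pivotal trial, and an effect measure with its uncertainty is what that calculation needs.

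There is a second cost. Two permitted analyses of the same data differ about twofold in power, and nothing in the plan stops the choice being made after the results are seen.

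**Working it through.** **Inputs.** From the documents: two arms, up to 50 patients, seven categories, and the three tests in Section 12. Assumed, because the documents do not give them: 1:1 allocation (25 per arm, with 20 per arm as a sensitivity case), a two-sided 5% level, the control-arm distribution (four shapes), and a proportional-odds shift with a common odds ratio of 2, 3 or 4. The plan has no power figure to reproduce.

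**Sparseness.** If responses spread evenly over the categories, the expected count per cell is 25 / 7 = 3.6. Any uneven distribution makes some cells smaller. Counts this low would probably lead the analyst to Fisher's exact test.

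**Simulated power.** There were 4,000 trials per setting (1,000 for Fisher). The tests were a t-test on scores 1 to 7, a tie-corrected Wilcoxon rank-sum test, Pearson chi-square on the 2×7 table (degrees of freedom = non-empty categories − 1), and the Fisher–Freeman–Halton exact test. Results at odds ratio 3, 25 per arm:

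| Control shape | Wilcoxon | t-test | Chi-square | Fisher | Chi-square / Wilcoxon |
|---|---|---|---|---|---|
| Uniform | 0.580 | 0.583 | 0.274 | 0.297 | 0.47 |
| Bell | 0.553 | 0.545 | 0.236 | 0.293 | 0.43 |
| Skewed | 0.546 | 0.504 | 0.247 | 0.323 | 0.45 |
| Concentrated | 0.533 | 0.475 | 0.273 | 0.361 | 0.51 |

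A separate run with other control shapes gave 23–27% for chi-square, 56–58% for Wilcoxon and 55–57% for the t-test at the same odds ratio.

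Ranges over the four shapes, 25 per arm:

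| Odds ratio | Wilcoxon | t-test | Chi-square | Fisher |
|---|---|---|---|---|
| 2 | 0.25–0.28 | 0.22–0.28 | 0.10–0.12 | 0.12–0.16 |
| 3 | 0.53–0.58 | 0.48–0.58 | 0.24–0.27 | 0.29–0.36 |
| 4 | 0.73–0.77 | 0.65–0.76 | 0.38–0.44 | 0.45–0.53 |

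**Share of Wilcoxon power kept, odds ratios 2 to 4.**
- Chi-square: 36–60%, a loss of 40–64%.
- Fisher: 45–73%, a loss of 27–55%.
- t-test: 89–101%, a loss of at most about 11%, largest for the concentrated shape.
- At 20 per arm: 34–57%, 38–70% and 90–103%.

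With no effect, the t-test rejected in 0.041–0.052 of trials at 25 per arm, so it holds its level on this scale.

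**Analytic cross-check.** With the same noncentrality, a test on 6 degrees of freedom has less power than one on 1. Noncentrality 7.85 gives 80% on 1 degree of freedom and 52% on 6. Noncentrality 3.84 gives 50% and 26%. This agrees with the simulation in direction and rough size.

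**Value of the baseline score.** Adjusting for a baseline that has correlation r with the outcome multiplies the residual variance by 1 − r². At an assumed r = 0.5 the factor is 0.75. A test with 50% power has a standardised effect of 1.96. After adjustment this becomes 1.96 / √0.75 = 2.26, and power is Φ(2.26 − 1.96) = Φ(0.30), about 62%. Simulation of a baseline-adjusted ordinal analysis gave about 60% against 50%. A t-test on change scores would not give this gain at r = 0.5, because the variance of the change is 2σ²(1 − 0.5) = σ², the same as without baseline.

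**The case against.** The strongest reply is that a planned test does fit. The t-test on scores 1 to 7 keeps its level and nearly all of the Wilcoxon power. A reader might infer from the sparse table that the Likert score suits neither planned test, or that the plan as written gives up half its power. The documents support neither inference. Section 12 does not send the score to chi-square any more than it sends it to the t-test. The wording about event rates suggests that the categorical rule was written with events in mind. Section 4 also lists the Likert item beside the visual analog scale (VAS), which is plainly continuous. This part of the reply stands, and it makes the loss conditional.

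Two further points stand in part. First, Section 12 reports counts by category, from which an unadjusted common odds ratio could be worked out later, and the VAS supplies a mean and standard deviation. Planning information is therefore not destroyed, but the plan does not commit to the estimate, and marginal counts cannot give a baseline-adjusted one. Second, this is a pilot with no named primary endpoint and no confirmatory dyspnea hypothesis, so the power of a test is a weak yardstick. That limits the importance. It does not remove the gap, because the gain in precision from baseline serves estimation as well.

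**Conclusion.** The concern holds in a conditional form. Section 12 leaves the Likert score unassigned. If it goes down the categorical route, an unordered chi-square test has about 23–27% power where an ordinal test has 53–58% (odds ratio 3, 25 per arm), and the loss with Fisher's exact test is 27–55%. If it goes down the continuous route, little is lost. On either route, as stated, the baseline score in Table 1 goes unused, at a cost of roughly 10 points of power if the baseline correlation is 0.5.

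The sizes rest on assumed 1:1 allocation, a two-sided 5% level, assumed response distributions and a consistent proportional-odds shift. The relative loss shrinks as the effect grows. What does not depend on these assumptions is that the plan permits two analyses of very different sensitivity and does not choose between them. For a pilot this is a worthwhile, inexpensive correction.

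**What to change.** In Section 12:

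- Exclude the Likert score from the unordered chi-square/Fisher rule.
- Name one time point from Table 1 for the between-arm comparison.
- Analyse the score there by an ordinal method adjusted for baseline: a proportional-odds model, or a rank ANCOVA. Enter baseline as a single linear or rank term, because separate baseline categories would be too sparse in about 50 patients.
- Report a common odds ratio, or the probability of a better score, with a 95% confidence interval.
- Keep an unadjusted Wilcoxon rank-sum test as a sensitivity analysis. A plain Wilcoxon test cannot adjust for baseline, so it should not be the main analysis.
- Analyse the VAS by ANCOVA with its baseline value.
- State the anchors and direction of the Likert item. If it asks about change since baseline, adjust for the baseline VAS instead.

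The physician questionnaire should stay outside this rule, since the documents do not give its response format.

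The cost is a few sentences and no new data. The one small downside is that the proportional-odds assumption and sparse categories need a check at this sample size. The plan should say in advance what will be done if the check fails, for example a fall-back to rank ANCOVA.

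### Section 10 limits risk to the IV line and radiation, which both arms share, and leaves out the consequences of BVA-prompted treatment changes; their recording and comparison by arm are not assured.

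*Combined protocol and SAP*

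**What the plan says.** Section 10 (Risk/Benefit Assessment) gives a closed list: "Risks are limited to the intravenous line placement, and radiation exposure". It then says that the new data go back to patient and provider and may lead to altered care. The next sentence begins: "However the study or protocol does not have an influence on the clinical care the patient will receive".

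Section 4 (Design & Procedures) randomizes patients to an unblinded, BVA-guided arm or a blinded, standard-of-care arm. BVA is scheduled for everyone near admission and before discharge; only disclosure and advice differ. On advice, Section 4 says: "In the BVA- guided arm the medical team will also be provided with data to inform the medical management of their patients". It adds a volume target ("The current data supports that ideal patient-specific euvolemic target should be 8-10% above euvolemia") and a red-cell prompt ("if there is a red-cell deficit of >20% the team in encouraged to consider therapies to augment the red blood cell pool"), and says that red-cell overload should ideally be addressed. Recommendations are non-binding and treatment is left to the physician. Objective A in Section 3 is to study how unblinded results affect treatment choices and clinical endpoints.

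Section 13 (Data & Safety Monitoring) opens: "Significant adverse events associated with the study procedures are not expected". Complications, if any, go to the IRB within 10 working days or per IRB policy, and side effects or problems are reported annually. Table 1 has no row for adverse events. Section 12 gives generic tests and names no safety outcome.

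**The concern.** A guided strategy can do harm only in the ways it changes treatment: volume management that turns out wrong for the patient, or consequences of red-cell therapy or removal. Section 10 excludes these by saying that risks are limited to two items, neither of which depends on the arm. Nothing later in the plan puts them back. No section defines an adverse event, schedules its collection or specifies a safety table by arm.

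Section 4 says the pilot is meant to inform the design, treatment recommendations and sample size of a pivotal trial. Advice on how to act on BVA results needs an account of what happened, by arm, when clinicians acted on them. As written, whether that account exists depends on how individual staff read undefined terms. Section 7 also promises that candidates will be told the risks of taking part, so the risk statement in Section 10 should be complete.

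**Working it through.** The point is mainly textual. The plan has no safety figure to reproduce, and its N of 50 comes with no alpha, power, event rate or allocation ratio, so that cannot be re-derived either.

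**Step 1: which risks can differ by arm.**

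| Source of risk | Guided arm | Blinded arm | Named in Section 10? |
|---|---|---|---|
| IV lines | yes | yes | yes |
| I-131 albumin | yes | yes | yes |
| Treatment changed because of a BVA result | possible | not by design (result withheld) | no |

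The two named risks cancel in a comparison of arms. The unnamed one is the contrast under study.

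**Step 2: Section 10 against itself and the design.** One sentence allows that BVA data may change care; the next says that the study does not influence care. Objective A presupposes that treatment choices may change. So does the physician questionnaire in Section 4, which asks whether unblinded results will alter management.

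**Step 3: follow one event through the plan.** Suppose kidney function worsens after a BVA-prompted change.
- *Data:* the basic metabolic panel is scheduled at baseline, day 1, day 3 and the day before discharge, so the value would probably be on file.
- *Recording as an adverse event:* Table 1 has no row for it.
- *Reporting:* it goes to the IRB if someone judges it a complication, a problem or reportable under IRB policy. The protocol does not define the first two. Section 13 opens with study procedures, Section 9 lists only tests and measurements as interventions, and the only potential complication listed in Section 4 is the radiation dose.
- *Comparison:* Section 12's tests could be applied, but no safety outcome is named.

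The data largely exist; the steps that turn them into a safety account by arm do not.

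**Step 4: what a comparison could show.** Assume 1:1 allocation (not stated): 50 / 2 = 25 per arm.
- If no event is seen in an arm, the one-sided 95% upper limit is 1 − 0.05^(1/25) = 0.113. Zero events in 25 is compatible with a true rate of up to 11.3%.
- At a common rate of 10%, the 95% interval for the difference has half-width 1.96 × √(2 × 0.1 × 0.9 / 25) = 0.166, or about 17 percentage points. At 20% it is 1.96 × √(2 × 0.2 × 0.8 / 25) = 0.222.
- Power of Fisher's exact test at two-sided 0.05, by full enumeration:

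| True rates | Power |
|---|---|
| 10% vs 20% | 9% |
| 20% vs 40% | 23% |
| 30% vs 50% | 23% |
| 10% vs 30% | 31% |

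These rates are illustrative; the documents give none. The table should estimate, not test.

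**Step 5: the volume target.** Section 2 reports that 34% of patients admitted with decompensated heart failure were hypovolemic or euvolemic. Applied to 25 guided patients, 0.34 × 25 = 8.5, so roughly 8 or 9. Section 4 does not say how a target of 8-10% above euvolemia applies to a patient measured below it.

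**The case against.** The strongest reply is that Section 13 does not confine reporting to procedures. Only its opening expectation does; the 10-working-day rule and the annual report are worded openly, and IRB policy may cover more. This stands. A reader might infer that treatment-related harms would not be reportable, but the text supports only that the terms are undefined.

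Second, the intervention is disclosure with non-binding information, not mandated treatment, so the sentence denying influence on care may mean only that the protocol does not dictate care. That is a fair reading and a good basis for rewording. It does not rescue the closed risk list, since advice offered to inform treatment can have consequences even when it is optional.

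Third, metabolic panel, vital signs, orthostatic vitals, urine output, dyspnea, medications and 30-day vital status are collected without restriction by arm, and clinical endpoints are part of objective A. This also stands. A reader might infer that harms would go uncompared, or that the pilot would declare the strategy safe without looking; the documents say neither.

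Three further inferences are unsupported. No passage gives a harm rate for guided treatment, so none can carry the argument. The 34% does not show that every such patient starts below the target, because no euvolemic band is defined. Nor is a renewal date given, so it cannot be shown that the annual report would come too late, and nothing in the documents requires an interim safety review.

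**Conclusion.** The point holds in this form. Section 10 sets a limit on risk that the design contradicts: it names two risks shared by both arms and omits the only one that can differ. Its two sentences on care conflict. With complications undefined, no adverse-event row and no safety outcome, recognition, reporting and comparison by arm of harms of BVA-guided treatment are not assured. That is weaker than saying they would be missed.

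This is more than missing detail, because an explicit statement of risk is wrong for the trial described and the pilot is meant to inform a later one. The conclusion rests on the text and on BVA being done in both arms, which Section 4 and Table 1 support. It does not depend on an assumed harm rate. The 25 per arm assumes equal allocation and bears only on the form of the comparison.

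**What to change.** 1. **Section 10.** Reconcile the two sentences on care with Section 3 (objective A) and Section 4, for example by saying that advice is non-binding but may change care. Name the consequences of BVA-prompted treatment changes as a risk of the guided arm.
2. **Section 13 and Table 1.** Define adverse events and record them in both arms, whether or not attributed to a study procedure, from the first BVA to the 30-day call. Use the data already scheduled, plus red-cell therapy or removal abstracted from the chart.
3. **Section 12.** Present counts and percentages by arm with confidence intervals, labelled as descriptive.
4. **Section 4.** The sponsor should reconcile how the stated volume target applies to patients measured below it. No clinical rule is proposed here.

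The cost is protocol wording, an adverse-event row, a few chart fields and one table, with no new tests or visits. The downside is that the table will include events due to heart failure itself, which a sample of this size cannot reliably separate from effects of guidance; the report should say so.
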